#### Pharmacogenetic Research Objectives

The objective of the PGx research (if there is a potential unexpected or unexplained variation) is to investigate a possible genetic relationship to handling or response to the combination treatment of dutasteride and tamsulosin or tamsulosin monotherapy. If at any time it appears there is potential variability in response in this clinical study or in a series of clinical studies with the combination treatment of dutasteride and tamsulosin or tamsulosin monotherapy that may be attributable to genetic variations of subjects, the following objectives may be investigated:

- Relationship between genetic variants and safety and/or tolerability of study treatment
- Relationship between genetic variants and efficacy of study treatment]

#### **Study Population**

Any subject who has given informed consent to participate in the clinical study, has met all the entry criteria for the clinical study, and receives study treatment may take part in the PGx research. Any subject who has received an allogeneic bone marrow transplant must be excluded from the PGx research.

Subject participation in the PGx research is voluntary and refusal to participate will not indicate withdrawal from the clinical study. Refusal to participate will involve no penalty or loss of benefits to which the subject would otherwise be entitled.

#### **Study Assessments and Procedures**

A whole blood sample (~6mL) will be collected for the PGx research using a tube containing EDTA. It is recommended that the blood sample be taken at Baseline (the first opportunity after a subject has been randomized and provided informed consent for PGx research), but may be taken at any time while the subject is participating in the clinical study. For the purposes of this trial, the PGx sample will be collected at Visit 2 (Baseline). However if the investigators deems it appropriate, the PGx sample may be taken at a later visit.

The PGx sample is labelled (or "coded") with a study specific number that can be traced or linked back to the subject by the investigator or site staff. Coded samples do not carry personal identifiers (such as name or social security number). The blood sample is taken on a single occasion unless a duplicate sample is required due to inability to utilize the original sample.

The DNA extracted from the blood sample may be subjected to sample quality control analysis. This analysis will involve the genotyping of several genetic markers to confirm

the integrity of individual samples. If inconsistencies are noted in the analysis, then those samples may be destroyed.

The need to conduct PGx analysis may be identified after a study (or set of studies) of dutasteride or tamsulosin treatment or studies on prostate-related disease has been completed and the study data reviewed. In some cases, the samples may not be studied. e.g., no questions are raised about how people respond to dutasteride or tamsulosin.

Samples will be stored securely and may be kept for up to 15 years after the last subject completes the study or GSK may destroy the samples sooner. GSK or those working with GSK (for example, other researchers) will use samples collected from the study for the purpose stated in this protocol and in the informed consent form.

Subjects can request their sample to be destroyed at any time.

#### **Subject Withdrawal from Study**

If a subject who has consented to participate in PGx research and has a sample taken for PGx research withdraws from the clinical study for any reason other than lost to follow-up, the subject will be given the following options:

- The sample is retained for PGx research.
- Any PGx sample is destroyed.

If a subject withdraws consent from the PGx research or requests sample destruction for any reason, the investigator must complete the appropriate documentation to request sample destruction within the timeframe specified by GSK and maintain the documentation in the site study records. In either case, GSK will only keep study information collected/generated up to that point.

#### Screen and Baseline Failures

If a blood sample for PGx research has been collected and it is determined that the subject does not meet the entry criteria for participation in the clinical study, then the investigator must complete the appropriate documentation to request sample destruction within the timeframe specified by GSK and maintain the documentation in the site study records.

#### **Pharmacogenetics Analyses**

1. Specific sections of DNA may be selected from areas of the genome (e.g., candidate genes) known to encode the drug target, drug metabolizing enzymes, areas associated with mechanisms underlying response or adverse events, and those linked to study disease and, thus, linked to drug response. In addition, continuing research may identify other enzymes, transporters, proteins or receptors that may be involved in response to dutasteride and tamsulosin or tamsulosin monotherapy. The genes that may code for these proteins may also be studied..

2. DNA Sequence analysis may be performed to determine genetic associations and interactions with treatment response

The results of PGx investigations will be reported either as part of the main clinical study report or as a separate report. All endpoints of interest from all comparisons will be descriptively and/or graphically summarized as appropriate to the data. In all cases, appropriate statistical methods will be used to analyze the genetic markers in the context of other clinical data. Statistical methods may include, but are not limited to Hardy-Weinberg Equilibrium testing, Comparison of Demographic and Baseline Characteristics by Genotype, Evaluation of Genotypic Effects, Evaluation of Treatment by Genotype and Gene-Gene Interaction, Linkage Disequilibrium, Multiple Comparison and Multiplicity and/or Power and Sample Size Considerations. Detailed description of the analyses to be conducted will be documented in the Pharmacogenetics Reporting and Analysis Plan.

#### **Informed Consent**

Subjects who do not wish to participate in the PGx research may still participate in the clinical study. PGx informed consent must be obtained prior to any blood being taken for PGx research.

#### Provision of Study Results and Confidentiality of Subject's PGx Data

GSK may summarize the cumulative PGx research results in the clinical study report.

In general, GSK does not inform the investigator, subject or anyone else (e.g., family members, study investigators, primary care physicians, insurers, or employers) of the PGx research results unless required by law. The information generated from PGx research is preliminary in nature, and the significance and scientific validity of the results are undetermined at such an early stage of research.

# 12.2. Appendix 2: Study Assessment Schedule In Order of Performance

# ALL SUBJECTS MUST SIGN AN INFORMED CONSENT PRIOR TO ANY STUDY MEASUREMENTS/PROCEDURES.

#### **Visit 1 (Pre-Screening Visit 1a and Screening Visit 1b)**

During Screening (Visits 1a and 1b) the procedures listed below will be completed in the **following sequential order when possible.** It is important that the IPSS questionnaire be administered first.

#### Visit 1a (Pre-screening)

- 1. Obtain informed consent from subject
- 2. Administer patient self-assessment questionnaires: International Prostate Symptom Score [IPSS], BHS Q8 BPH Impact Index [BII]
- 3. Administer suicidality questionnaire [C-SSRS]
- 4. Complete medical history, Cardiovascular history and demographics
- 5. Review concomitant medications
- 6. Measure peak urinary flow
- 7. Measure post void residual volume
- 8. Review inclusion/exclusion criteria for patient eligibility
- 9. Call RAMOS to register subject and obtain unique registration number
- 10. Collect blood samples for clinical laboratory tests including PSA
- 11. Schedule next clinic visit to complete screening procedures

#### Visit 1b (Placebo run-in)

Visit 1b should be conducted a maximum of 14 days after V1a (allowing sufficient time for lab results from V1a to be returned to site).

- 1. Review pre-screening PSA/laboratory results
- 2. Administer Problem Assessment Scale of the Sexual Function Index (PAS-SFI)
- 3. Perform physical examination, including digital rectal exam, qualitative breast examination, height, weight, and vital signs blood pressure and pulse after 5 mins sitting
- 4. Obtain a 12-lead electrocardiogram (after 5 mins supine)
- Assess SAEs
- 6. Measure peak urinary flow (if required)
- 7. Measure post void residual volume (if required)

- 8. Measure prostate volume by transrectal ultrasound (TRUS) if suitable TRUS not available
- 9. Review inclusion/exclusion criteria, including concomitant medications, and confirm patient eligibility
- 10. Call RAMOS
- 11. Dispense placebo run-in medication and provide dosing instructions
- 12. Schedule next clinic visit

#### Visit 2 (Baseline/Randomisation)

Visit 2 should be conducted 28 days ( $\pm$  4 days) after Visit 1b. For each subject, all visits should be scheduled at a similar time of day: morning or afternoon. During Visit 2 the procedures listed below will be completed in the following sequential order:

- 1. Administer patient self-assessment questionnaires: International Prostate Symptom Score [IPSS], BHS Q8,BPH Impact Index [BII], Problem Assessment Scale of the Sexual Function Index (PAS-SFI)
- 2. Review concomitant medication and assess continuing eligibility
- 3. Record any episodes of AUR or prostatic surgical and minimally-invasive/non-surgical interventions along with associated resource utilization.
- 4. Record any episodes of UTI/urosepsis, urinary incontinence (first episode or consistent worsening), and renal insufficiency
- 5. Collect blood samples for PGx and HBsAG and Hepatitis C Antibody
- 6. Measure vital signs: blood pressure and pulse after 5 mins sitting
- 7. Assess AEs
- 8. Measure peak urinary flow
- 9. Measure post void residual volume
- 10. Call RAMOS to randomize subject
- 11. Collect unused placebo run-in medication and assess compliance
- 12. Dispense a 3-month supply (of blinded study medication and provide dosing instructions
- 13. Schedule next clinic visit

#### **Visit 3 (3 months post-randomisation)**

Visit 3 will be conducted 13 weeks (± 14 days) after Visit 2. For each subject, all visits should be scheduled at a similar time of day: morning or afternoon. The following study procedures will be conducted:

1. Administer patient self-assessment questionnaires: International Prostate Symptom Score [IPSS], BHS Q8, BPH Impact Index [BII],

- 2. Review concomitant medication and assess continuing eligibility
- 3. Measure vital signs after 5 mins sitting
- 4. Chinese origin subjects, recuited in China only: Blood sample for PPK
- 5 Assess AEs
- 6. Record any episodes of AUR or prostatic surgical and minimally-invasive/non-surgical interventions along with associated resource utilization.
- 7. Record any episodes of UTI/urosepsis, urinary incontinence (first episode or consistent worsening), and renal insufficiency
- 8. Collect unused study medication and assess compliance
- 9. Call RAMOS and Dispense a 3-month supply of study medication
- 10 Schedule next clinic visit

#### **Visit 4 (6 months post-randomisation)**

Visit 4 will be conducted 26 weeks ( $\pm$  14 days) after Visit 2. For each subject, all visits should be scheduled at a similar time of day: morning or afternoon. The following study procedures will be conducted:

- 1. Administer patient self-assessment questionnaires: International Prostate Symptom Score [IPSS], BHS Q8, BPH Impact Index [BII]
- 2. Administer suicidality questionnaire [C-SSRS]
- 3. Review concomitant medication and assess continuing eligibility
- 4. Perform physical examination, including digital rectal exam, qualitative breast examination and vital signs blood pressure and pulse after 5 mins sitting
- 5. Collect blood sample for PSA
- 6. Chinese origin subjects, recuited in China only: Blood sample for PPK
- 7. Assess AEs
- 8. Record any episodes of AUR or prostatic surgical and minimally-invasive/non-surgical interventions along with associated resource utilization.
- 9. Record any episodes of UTI/urosepsis, urinary incontinence (first episode or consistent worsening), and renal insufficiency
- 10. Measure peak urinary flow
- 11. Measure post void residual volume
- 12. Collect unused study medication and assess compliance
- 13. Call RAMOS and Dispense a 3-month supply of blinded study medication
- 14. Schedule next clinic visit

ARI114265

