# 7. STUDY ASSESSMENTS AND PROCEDURES

A signed, written informed consent form must be obtained from the subject prior to any study-specific procedures or assessments.

Refer to the Time and Events Table for the timing of all assessments (Table 1). Details on efficacy and safety assessments are presented in Section 7.2 and Section 7.3 respectively. Further details of study procedures and assessments can be found in the study procedures manual (SPM).

For health outcome measures refer to Section 7.5, for PGx samples refer to Appendix 1

Unscheduled visits/assessment may be performed by the investigator as medically necessary.

Investigators may be requested to perform additional safety tests during the course of the study based on newly available data to ensure appropriate safety monitoring. Appropriate local regulatory and ethical approvals should be obtained before any additional testing is performed.

Table 1 Time and Events Table

Study Procedures	Visit 1a Pre- Screen Pre-Screen Visit	Visit 1b** Screening (V1a + 14 days) Start of Placebo run-in	Visit 2 Baseline (V1b + 28d ± 4 days)  Start of Treatment Phase Baseline (Randomisation)	Visit 3 (Baseline + 13 wks ± 14 days) 3 months post Randomisation (Rand)	Visit 4 (Baseline + 26 wks ± 14 days) 6 months post Rand	Visit 5 (Baseline + 39 wks ± 14 days) 9 months post Rand	Visit 6 (Baseline + 52 wks ± 14 days) 12 months post Rand	Visits 7 - 9 (Years 2, repeat as for V3-V5 of Year 1) 15,18 & 21 months post Rand respectively	Visit 10 (Baseline + 104 wks ± 14 days) End of Treatment Phase 24 months post Randi
ICF	X								
Incl/Exclusion	X	X							
Medical Hx/ Demog/CV Hx/	X								
ECG (12-lead)		X							
Collection of PGx Sample			Χ						
Safety evaluations									
Concomitant medication	X	X	X	X	X	X	X	$\Rightarrow$	Χ
Physical Examinationa		Χ			X		Χ	Xh	Χ
Vital signs b		X	X	X	X	Χ	Χ	$\Rightarrow$	Χ
Haematology/clinical chemistry	X						Х		Х
HBsAG and Hepatitis C Antibody 			Χ						
Total serum PSAc	Х				Х		Х		Х
Post-void residual volume (PVR)	X	X***	X		Х		Χ	Xh	Х
AEs d		X	Χ	Х	Х	Х	Χ	$\Rightarrow$	Х
Suicidality (C-SSRS)	Х				X		X		Х
Efficacy:									
BPH symptoms (IPSS)	Х		Х	Х	Х	Х	Х	$\Rightarrow$	Х
Prostate Volume (TRUS)		X					Χ		Х
Peak Urine Flow (Qmax)	Х	X***	Χ		Х		Χ	Xh	Х
AUR or BPH-related Surgery			Х	Х	Х	Х	$\Rightarrow$	Х	Х

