## 7.2.2.5. End of Study Treatment Assessments

During the study period that is between the scheduled visits, if a subject discontinues study treatment permanently after Visit 2 (post-randomisation) for any reason, other than lost to follow-up, the investigator should make every effort to schedule a visit by the subject to the study site and complete the following assessment:

- Concomitant medications
- Adverse events
- Physical exam including vital signs, DRE and qualitative breast examination
- Obtain blood samples for hematology, clinical chemistry and PSA determinations
- Administer health outcome questionnaires (IPSS, BHS,BII and PAS-SFI)
- Administration of C-SSRS questionnaire
- Record any episodes of AUR, and, BPH-related prostatic surgery or minimally-invasive/non-surgical interventions
- Record any episodes of UTI/urosepsis, urinary incontinence (first episode or consistent worsening), and renal insufficiency
- Retrieve any unused double-blind study medication, assess compliance and record date of last dose of study medication
- Discuss the biannual follow-up phone call schedule
- Complete subject eCRF

If the decision for a subject's study treatment discontinuation is made during a regularly scheduled visit, the procedure that are stated above should be completed, in addition to any scheduled procedure that is not listed above.

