## 7.3.4.2. Prostate Specific Antigen (PSA)

Total serum PSA concentrations will be assessed at Pre-screening Visit 1a and post-randomisation at Visit 4, (Month 6), and annually at Visits 6 and 10. For total PSA, the actual value will be reported at Pre-screening; an adjusted value will be reported for all assessments after 6 months of treatment – see below.

A number of clinical situations (e.g. prostatitis, biopsy, prostatic abscess) can cause transient rises in PSA. Therefore, blood samples for evaluating PSA levels must be collected within the study-defined time windows and prior to performing any clinical procedures (i.e. TRUS and DRE). If a situation arises requiring interim intervention, PSA determinations must be postponed for a period of 1 month following any procedure performed on the prostate and for 3 months following initiation of treatment for acute bacterial prostatis.

Screening PSA results will be reported immediately to the investigators to determine eligibility of study subjects. All post-baseline PSA levels will subsequently be reported following blinding adjustment of the PSA result (where appropriate) as described below.

In order to maintain investigator blinding to study treatment, an independent reviewer who is unblinded to the PSA results as well as the drug random code, will adjust PSA values for appropriate participants. After a subject completes six month of treatment, PSA results will be reported to the principal investigators using the following methods: (1) for subjects on tamsulosin monotherapy, the actual PSA value will be reported; (2) for subjects receiving combination therapy, the PSA value will be multiplied by two (x 2) to account for the known effect of 5ARI's on reducing PSA (data from Phase IIIa and CombAT studies of dutasteride in BPH patients demonstrated a decrease in serum PSA levels by approximately 50% after 6 months of treatment). In dutasteride-treated subjects receiving combination therapy, the doubled PSA value will be randomly stated as the doubled value or a value 0.1 units higher or lower, so that all doubled values expressed to one decimal place will not automatically be reported as an even number.

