**Note**: Dutasteride reduces total serum PSA concentration by approximately 40% following 3 months of treatment and by approximately 50% following 6, 12, and 24 months of treatment. PSA measurements should not be performed prior to 6 months of treatment because of the variable effect of dutasteride on serum PSA during this time. Although discouraged, if an additional PSA measurement outside the scheduled assessments is necessary, it should be assayed through the study central laboratory.

Central laboratory, study sites, and monitors will remain blinded to treatment assignments throughout the duration of the study.

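### Visit 4 and the end-of-treatment lists name the rectal examination before the PSA draw, against the protocol's own rule, and no rule says how PSA drawn before six months is masked from sites

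*Protocol*

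**What the plan says.** **Order of procedures.** Appendix 2 of the Protocol is headed "Study Assessment Schedule In Order of Performance". At Visit 4 its consecutive steps are "4. Perform physical examination, including digital rectal exam, qualitative breast examination" and "5. Collect blood sample for PSA". Section 7.3.4.2 states that "blood samples for evaluating PSA levels must be collected within the study-defined time windows and prior to performing any clinical procedures (i.e. TRUS and DRE"). Section 7.3.4 sets the same order for all laboratory blood. At Visits 6 and 10, Appendix 2 puts the blood draw at step 3 and the examination at step 5. The unnumbered end-of-treatment lists, in Section 7.2.2.5 and at the end of Appendix 2, name the DRE before the bloods.

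**Masking of PSA.** Section 7.3.4.2 begins its reporting method thus: "After a subject completes six month of treatment, PSA results will be reported to the principal investigators using the following methods". The method is the actual value on tamsulosin alone, and the doubled value, randomly shifted by up to 0.1 units, on combination. An independent unblinded reviewer makes the adjustment. A note in the same section says "PSA measurements should not be performed prior to 6 months of treatment because of the variable effect of dutasteride".

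**PSA before six months.** Three routes exist:
- The Visit 4 column of Table 1 reads "Visit 4 (Baseline + 26 wks ± 14 days) 6 months post Rand".
- The end-of-treatment visit, due at permanent discontinuation at any time after Visit 2, includes "Obtain blood samples for hematology, clinical chemistry and PSA determinations".
- Section 7.3.4.2 discourages off-schedule PSA but allows it through the central laboratory.

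**The concern.** A site that follows Appendix 2 step by step at Visit 4 breaches Section 7.3.4.2, and a site that follows Section 7.3.4.2 departs from the appendix. Change in PSA is a safety endpoint (Section 7.3.1), and a clinically significant rise is a named trigger for a for-cause biopsy (Section 7.3.8). The screening value is drawn at Visit 1a and the first DRE is done at Visit 1b, so a post-DRE value would be compared with a pre-DRE baseline.

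The masking gap is the weightier part. Tamsulosin is open label (Section 5.5), so dutasteride versus placebo is the only blind in the trial, and PSA is the routine measurement most able to reveal it. The investigator holds the true screening PSA. An early value that reached the site unadjusted could disclose the arm while that investigator is still judging adverse event causality and the BPH-relatedness of urinary and renal events. Retention and surgery, which are secondary endpoints, are followed to two years even after treatment stops.

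**Working it through.** **1. The plan's own factor.** Section 7.3.4.2 gives a PSA fall of about 40% at 3 months and about 50% at 6, 12 and 24 months. The neutral multiplier is 1/(1 − reduction). At six months it is 1/(1 − 0.50) = 2.00, which reproduces the stated doubling.

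**2. Order of procedures (no arithmetic).**

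| Place | PSA or blood draw | DRE | Agrees with 7.3.4 and 7.3.4.2? |
|---|---|---|---|
| Visit 4 | step 5 | step 4 | no |
| Visit 6 | step 3 | step 5 | yes |
| Visit 10 | step 3 | step 5 | yes |
| End-of-treatment lists | named after DRE | named first | no (unnumbered) |

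To scale a possible effect, assume the DRE raises PSA by 0-20%; the documents give no figure. At the upper end, change from baseline on tamsulosin moves from 0% to +20%. On combination, 0.50 × 1.20 = 0.60, so −50% becomes −40%. The ratio between arms stays 0.50.

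**3. How early the draws can fall.** Visit 4 is at 26 × 7 = 182 days ± 14, that is days 168 to 196. Six calendar months are 365.25/2 = 182.6 days, so a draw inside the window can be up to about two weeks early. End-of-treatment and off-schedule draws can come at any time after randomisation.

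**4. What an unadjusted value would show.** As a fraction of baseline, combination gives 1 − 0.40 = 0.60 at 3 months and 1 − 0.50 = 0.50 at 6 months. Linear interpolation from week 13 to week 26 (an assumption) gives a 48.5% fall at week 24, a ratio of 0.515. Tamsulosin alone is taken as 1.0. For a baseline of 4 ng/mL the combination values are 2.4 and 2.0.

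**5. Chance of guessing the arm.** Let r be the ratio to baseline. The standard deviation of the log ratio of two measurements is s = √(2 ln(1 + CV²)). With a cut at the midpoint on the log scale, the proportion correct is Φ(−ln r / (2s)). The within-subject CV is not in the documents, so a range is shown (chance is 50%):

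| CV | r = 0.60 (3 months) | r = 0.50 (6 months) |
|---|---|---|
| 15% | 89% | 95% |
| 20% | 82% | 89% |
| 30% | 73% | 80% |
| 40% | 68% | 74% |

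**6. How many subjects.** Section 9.2.1 assumes 20% discontinuation of 586, about 117. If 25-50% of these stop before Month 6 (an assumption), 117.2 × 0.25 = 29 to 117.2 × 0.50 = 59 subjects could have an early end-of-treatment PSA, about 15-29 per arm. The documents do not allow a count for the other two routes.

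**7. Can doubling simply start earlier?** At 3 months 0.60 × 2 = 1.20 of baseline, 20% too high; the neutral factor there is 1/0.60 = 1.67. At week 24, 0.515 × 2 = 1.03. Doubling is therefore close to neutral just before Visit 4 but not at 3 months.

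**The case against.** The strongest reply is that Section 7.3.4.2 says all post-baseline PSA values are reported after blinding adjustment, and that the laboratory, sites and monitors stay blinded throughout. A reader might infer from the six-month wording that earlier values go to sites raw, but the document does not say so. What stands against the reply is that the general sentence limits adjustment to cases where it applies and refers to a method that starts at six months. The intention to mask is clear; the means for early values is absent.

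The Visit 4 route is the weakest of the three. Table 1 labels the whole window as Month 6, and the amendment log shows that the Visit 4 PSA and the six-month start of adjustment came in together, so coverage of Visit 4 was evidently intended. About half the window's days precede six months, but that is not half the subjects, because the distribution of visits is unknown.

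A reader might also infer direct harm to 18 further months of the primary endpoint. The documents do not support this. After discontinuation only telephone follow-up for events is planned, and IPSS is taken at the end-of-treatment visit itself. For subjects still on treatment, IPSS is self-completed, the investigator may not interpret items, and test results should be withheld until it is done (Section 7.5.2).

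Nor do the documents show that PSA is in fact distorted or that needless biopsies would follow. No size is given for a DRE effect, it would act in both arms, and a biopsy rests on the investigator's judgement. PSA testing begins from the final assessment, where the order for completers is right. The Visit 4 text also lacks the explicit call for sequential order made at Visit 2, although the appendix title implies it.

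**Conclusion.** Both inconsistencies hold on the face of the Protocol. The procedure order at Visit 4 and in the end-of-treatment lists conflicts with Sections 7.3.4 and 7.3.4.2, so PSA there may be affected, by an amount the documents do not let one state. The reporting of PSA drawn before six months is undefined, although the Protocol requires such draws at early discontinuation and permits them by two other routes; the note against measuring PSA before six months conflicts with this.

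Unblinding is possible, not established. The 68-95% applies only if values are released raw and rests on the assumed CV of 15-40% and the approximate PSA falls in Section 7.3.4.2. The exposure is mainly to adverse event causality and event judgements, with an indirect path at most to IPSS. It should be corrected because it concerns the trial's only blind and the correction is small.

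**What to change.** 1. In Appendix 2, move the PSA draw ahead of the physical examination at Visit 4, and name the bloods before the examination in both end-of-treatment lists.
2. In Section 7.3.4.2, state that every post-randomisation PSA, including end-of-treatment, off-schedule and early Visit 4 values, goes to sites only through the independent unblinded reviewer. Give values before six months a masked-release rule of their own, not a plain backward extension of the doubling.
3. Reconcile the note against PSA before six months with the Visit 4 window and the end-of-treatment PSA, so that the three passages agree.

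The cost is amendment wording and one reporting rule for the central laboratory and the reviewer. Sample size, power and alpha do not change. The drawback is that masked early values will be less exact than those after six months, because the PSA fall is still changing.
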